4.5.3.2 Stage 2: Treatment with ACM or CM

Patients enrolled in Stage 2 will be randomized to either ACM or CM and will receive treatment as outlined below:

Stage 2: Randomized to ACM: Treatment with ACM over Days 1-9

Follow the Stage 1 treatment schema above

Stage 2: Randomized to CM: Treatment with CM over Days 1-4

- **Days 1, 2, and 3: cytarabine (C) - Continuous over 72 hours**
2 gm/m² by continuous IV infusion over 72 hours (± 2.5 hours)
(ie, 667 mg/m² daily for total of 2 gm/m²)
- **Day 4: mitoxantrone hydrochloride (M) is administered 12 hours after completion of cytarabine treatment**
40 mg/m² by IV infusion over 1-2 hours (± 10 minutes)

4.5.3.3 Evaluation After Cycle 1

- Patients who achieve CR, CRi, CRp, or PR after the first cycle (completion of all doses) may receive up to 3 additional optional cycles of treatment.
 - After completing the first cycle of treatment, continued use of mitoxantrone is optional.
 - Mitoxantrone must be omitted from subsequent cycles if the patient's lifetime daunorubicin equivalent exceeds 460 mg/m² (see *Appendix G* for conversion table) or the left ventricular ejection fraction (LVEF) drops below 45%.
- Patients not demonstrating evidence of CR, CRi, CRp, or PR after the first cycle of treatment will be considered for removal from the study, although with permission of the Medical Monitor, induction treatment may continue if clinically indicated and provided there is no evidence of toxicity \geq NCI CTCAE grade 4.
- Perform the End of Study Assessments for those patients who do not continue on study to receive at least one additional cycle of treatment (see *Section 5.5*).

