4.5.3.4 Crossover (Stage 2)

- Patients randomized to CM with progressive disease or no response after one cycle of CM may cross over to receive ACM.
- Patients randomized to CM with a best response of PR after 2 cycles of CM may also cross over to receive ACM.

- Continued use of mitoxantrone is optional after completion of one cycle of ACM
- Mitoxantrone must be omitted from subsequent cycles if the patient's lifetime daunorubicin equivalent exceeds 460 mg/m² (see *Appendix G* for conversion table) or the left ventricular ejection fraction (LVEF) drops below 45%. Patients crossing over who meet the above criteria will receive only AC (alvocidib and cytarabine) for all cycles instead of ACM.
- Patients who cross over to ACM may receive up to a combined total (CM + ACM) of 4 cycles.

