11.4.4 Safety Analyses

The following safety analyses will be performed on all patients who receive at least one dose of study drug.

- **30- and 60-day Mortality** = Estimates of 30- and 60-day mortality and their pointwise 95% CIs will be derived from Kaplan-Meier curves for OS by treatment arm
- **Adverse Events** = Reported AE terms will be mapped to MedDRA preferred terminology. All reported events will appear in AE listings, however only TEAEs will be summarized. A TEAE is an AE that starts or increases in severity any time after the first administration of any study drug up to 30 days following the last administration of any study drug. AE severity will be rated by the investigator according to NCI CTCAE version 4.03 in Stage 1 and version 5.0 in Stage 2 (see *Appendix C*).
- **Clinical Laboratory Assessments** = Laboratory test results measured on a continuous scale and changes from baseline values will be summarized by visit and within treatment arm using mean, standard deviation, median, minimum and maximum values. Categorical test results will be summarized within treatment arm using shift tables. Additionally, for tests where NCI CTCAE, version 4.03 in Stage 1 and version 5.0 in Stage 2 (see *Appendix C*), severity criteria are specified, NCI CTCAE severity grades will be summarized in shift tables.
- **Vital Signs** = Vital signs and changes from baseline values will be summarized by visit and within treatment arm using mean, standard deviation, median, minimum and maximum values.

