7.11.2. Adverse Events

Reported adverse event (AE) terms will be mapped to MedDRA preferred terminology. AEs suggestive of tumor lysis syndrome (TLS) will be flagged based in the standardized MedDRA query (SMQ) for TLS. All reported events will appear in AE listings, however only treatment-emergent adverse events will be summarized. A treatment-emergent adverse event (TEAE) is an AE that starts or increases in severity any time after the first administration of any study drug up to 30 days following the last administration of any study drug. AE severity was rated by the investigator according to Common Terminology Criteria for Adverse Events (CTCAE) version 4.03 criteria.¹³

A high-level safety summary will display the numbers of patients within each treatment arm and overall who experience one or more AEs in each of the following categories:

- All TEAEs regardless of severity or presumed relationship to study drug
- TEAEs judged related to study drug
- All TLS SMQ TEAEs
- TLS SMQ TEAEs judged related to study drug
- Treatment-emergent serious adverse events (SAEs)
- TEAEs leading to a delay in the administration of study drug
- TEAEs leading to a reduction in the protocol-specified dose of study drug
- TEAEs leading to discontinuation of study drug
- TEAEs leading to withdrawal from the study
- TEAEs leading to death

The base summary of TEAEs will show within- and between-treatment-arm incidence rates for each MedDRA primary SOC and/or PT by highest reported CTCAE severity grade and overall. A separate summary will be produced each of the AE subsets listed above. Additional AE summaries may be produced using safety data from subsets of patients and/or characterized using additional SMQs.

Partial start and end dates for adverse events will be replaced by calendar dates that maximize the duration of the adverse event. The following steps will be followed.

For a partial start date:

1. Replace a missing month with January
2. Replace a missing calendar day with the first of the month
3. If the replacement date is prior to the first dose of study drug, then set the adverse event start date equal to the date of the first dose

For a partial end date:

1. Replace a missing month with December
2. Replace a missing calendar day with the last day of the month

The replacement date for a missing end date may exceed end of the adverse event reporting period specified in the study protocol.

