7.11.4. Clinical Laboratory Parameters

Typical comparisons of results summarized by visit may have limited interpretability in this study because (1) study drugs from the two treatment arms are administered on

different cycle days (Days 1-9 for ACM versus Days 1-4 for CM), (2) the schedule for clinical laboratory evaluations (cycle day and frequency) is different between the treatment arms, and (3) additional cycles of treatment start according to patients' response to treatment rather than based on a predetermined schedule. Therefore, four groups of laboratory data will be summarized separately:

- Cycle 1 results (from all patients in the safety population) up to the day a patient starts Cycle 2 or 10 weeks after starting Cycle 1, whichever comes first
- Cycle 2 results (from patients in the safety population who receive at least 2 cycles of study drug) up to the day a patient starts Cycle 3 or 10 weeks after starting Cycle 2, whichever comes first
- Cycle 3 results (from patients in the safety population who receive at least 3 cycles of study drug) up to the day a patient starts Cycle 4 or 10 weeks after starting Cycle 3, whichever comes first
- Cycle 4 results (from patients in the safety population who receive 4 cycles of study drug) up to 10 weeks after starting Cycle 4

Laboratory test results measured on a continuous scale and changes from baseline values will be summarized within treatment arm using mean, standard deviation, median, minimum and maximum values. Results will be summarized at baseline, on Days 1-9, and every 7 days starting with Day 15 for patients receiving ACM, and at baseline, on Days 1-4, and every 7 days starting with Day 8 for patients receiving CM. Up to the point of starting a new treatment cycle or withdrawing from the study, a patient's most recent test result will be carried forward and included in analyses on days when clinical laboratory testing was not performed.

Ordinal categorical test results will be summarized within treatment arm using shift tables. Additionally, for tests where CTCAE [version 4.03] severity criteria are specified, CTCAE severity grades will be summarized in shift tables.

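### Adverse events are compared between arms over all cycles, with no Cycle 1 or exposure-adjusted table, so response-driven cycles and crossover can distort the comparison in either direction

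*SAP*

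**What the plan says.** SAP 7.11.2 defines a TEAE as an event that begins or worsens "any time after the first administration of any study drug up to 30 days following the last administration of any study drug". Protocol 11.4.4 has the same rule: an event that "starts or increases in severity any time after the first administration of any study drug", with the same 30-day end. The window therefore runs across every cycle a patient receives. On tabulation the SAP states: "The base summary of TEAEs will show within- and between-treatment-arm incidence rates for each MedDRA primary SOC" and/or preferred term, by highest grade. SAP Table 9 lists TEAE and SAE tables, none of them limited to Cycle 1, split by cycle or adjusted for exposure.

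The number of cycles is not fixed. Under Protocol 4.5.3.3, patients with CR, CRi, CRp or PR after Cycle 1 "may receive up to 3 additional optional cycles of treatment". Others are considered for removal, "although with permission of the Medical Monitor, induction treatment may continue if clinically indicated". Protocol 4.5.3.4 adds: "Patients randomized to CM with progressive disease or no response after one cycle of CM may cross over to receive ACM", with a cap of four combined cycles.

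SAP 7.11.4 recognises the difficulty for laboratory data. It notes that further cycles begin according to "response to treatment rather than based on a predetermined schedule" and summarises each cycle separately; SAP 7.11.5 does the same for vital signs. Table 9 has a Cycle 1 table for Cairo-Bishop tumor lysis syndrome (TLS), and SAP 7.11.1 gives 30- and 60-day mortality.

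**The concern.** A crude percentage of patients with an event rises with the number of cycles given. Here that number follows from response, the outcome on which the trial is designed to separate the arms, and from crossover, which only CM patients can take. Two regimens equally toxic per cycle would then show different TEAE and SAE percentages.

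The fourth objective in SAP 4.2 is to describe the safety of ACM, judged in relapsed/refractory patients relative to CM. The TEAE and SAE tables are the main evidence for events such as infection, diarrhea and cardiac toxicity. As planned, a reader cannot tell how much of any gap comes from toxicity and how much from unequal numbers of cycles.

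**Working it through.** **Inputs from the documents.** CR rates are 70% vs 30% (Protocol 11.2.2) and 70% vs 40% (SAP 5.1.2). Responders may take up to three extra cycles (Protocol 4.5.3.3). The last drug in a cycle is given on Day 9 for ACM and Day 4 for CM (Protocol 4.5.3.1, 4.5.3.2). For safety, the SAP keeps crossover patients in CM (7.1), whereas the protocol counts anyone given alvocidib as ACM (11.3).

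**Assumptions not in the documents.** Per-cycle event risk q is 10% to 30%, equal in both arms and all cycles, and independent between cycles. The CR rate stands in for the share of patients eligible for more cycles. Uptake of extra and crossover cycles is varied.

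**1. The plan's own figure.** The protocol's 28 per arm is not disputed; it supplies the response rates. With unpooled variance, n = (1.960 + 1.282)² × (0.7×0.3 + 0.3×0.7) / 0.4² = 27.6, so 28 per arm. It reproduces.

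**2. No crossover, all responders take 1, 2 or 3 extra cycles with equal probability.** Let S = [(1−q)² + (1−q)³ + (1−q)⁴]/3 and let c be the share continuing. Then incidence = 1 − [(1−c)(1−q) + c·S], and the gap between arms = (c_ACM − c_CM)(1 − q − S).

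At q = 30%, S = (0.49 + 0.343 + 0.2401)/3 = 0.3577. ACM: 1 − (0.3×0.7 + 0.7×0.3577) = 54.0%. CM at 30%: 1 − (0.7×0.7 + 0.3×0.3577) = 40.3%.

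| q | S | ACM | CM (30%) | Gap | CM (40%) | Gap |
|---|---|---|---|---|---|---|
| 10% | 0.7317 | 21.8% | 15.0% | 6.7 | 16.7% | 5.0 |
| 20% | 0.5205 | 39.6% | 28.4% | 11.2 | 31.2% | 8.4 |
| 30% | 0.3577 | 54.0% | 40.3% | 13.7 | 43.7% | 10.3 |

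Gaps are in percentage points, from unrounded values. Mean cycles are 1 + 2×0.7 = 2.4 on ACM, against 1.6 (30%) or 1.8 (40%) on CM.

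**3. Lower uptake, no crossover.** If half of responders take one extra cycle, the gap is (0.7 − 0.3) × 0.5 × q(1−q) = 0.2q(1−q), which gives 1.8, 3.2 and 4.2 points at q = 10%, 20% and 30%.

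**4. Crossover under the SAP grouping.** Let a share x of CM non-responders cross over and also take 1 to 3 more cycles. The gap becomes [0.7 − c − (1−c)x](1 − q − S), with c the CM rate.

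- With c = 0.3 it is zero at x = 0.4/0.7 = 57%. With c = 0.4 it is zero at x = 0.3/0.6 = 50%.
- At x = 100% it is −0.3(1 − q − S), that is −5.0, −8.4 and −10.3 points, so CM looks worse.
- If crossover patients take only one cycle (q = 30%, c = 0.3), the gap is 13.7 − 100 × 0.7x × 0.21: +6.3 at x = 50% and −1.0 at x = 100%.

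**5. Protocol grouping.** Take q = 30%, one extra cycle for every responder (CM rate 30%) and one crossover cycle for half of CM non-responders. Two-cycle risk is 1 − 0.7² = 51%. Per 100 randomized to each arm, 35 CM patients move to the ACM group:

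- ACM group: (70×0.51 + 30×0.30 + 35×0.51)/135 = 46.3%
- CM group: (30×0.51 + 35×0.30)/65 = 39.7%, a gap of +6.6 points
- SAP grouping, same scenario: 44.7% vs 43.65%, about +1 point

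**6. Cycle 1 only.** Each patient contributes one cycle. With equal follow-up and equal toxicity the expected result is q vs q, a gap of zero whatever the response or crossover rates.

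**7. Window for a one-cycle patient.** Thirty days after last dose is Day 9 + 30 = 39 on ACM and Day 4 + 30 = 34 on CM.

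**The case against.** The strongest objection is to the direction. A reader might infer that ACM must look more toxic simply because it produces more responders. The documents do not support that: CM failures may cross over, the SAP counts their alvocidib cycles in CM, and step 4 shows the excess vanishing or reversing. This stands. It does not rescue the tables, since any cancellation would come from alvocidib-exposed cycles sitting in the control arm.

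The size is also uncertain. Extra cycles are optional, some responders will go to transplant, and mitoxantrone may be dropped after Cycle 1, so risk may differ in later cycles. Eligibility to continue includes CRi, CRp and PR, for which neither document gives planned rates. The 7 to 14 points therefore belong to a high-uptake scenario. With 28 per arm, the standard error of 54% vs 40% is √(0.54×0.46/28 + 0.40×0.60/28), about 13 points, so the artefact could not be told from noise in this trial. It is nevertheless systematic, and an analysis choice removes it.

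A reader might also conclude that the plan has no like-for-like safety comparison, or that a test is invalidated. Neither holds. TLS, laboratory data, vital signs and early mortality have Cycle 1, per-cycle or fixed-time summaries, and cycles received are reported by arm (SAP 7.8). The SAP's table templates drop p-values for safety data.

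Finally, the SAP says: "Additional AE summaries may be produced using safety data from subsets of patients and/or characterized using additional SMQs". That is permission, and it names no restriction by cycle or time.

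**Conclusion.** The point holds as a gap in the descriptive safety analysis. TEAEs, SAEs and Grade 3 or higher events are compared only over all cycles, while exposure after Cycle 1 depends on response and crossover. At equal toxicity per cycle and without crossover, the false excess on ACM is about 2 to 4 points with low uptake of extra cycles (30% CM rate). With full uptake of one to three cycles it is 5 to 10 points (40% CM rate) or 7 to 14 (30%). Under the SAP grouping, crossover can bring it to zero or turn it to as much as 10 points against CM. These figures rest on assumed per-cycle risks of 10% to 30%, independence between cycles, and the CR rate as a proxy for continuing. The sign cannot be predicted from the documents. The change is worth making, although no hypothesis test depends on it.

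**What to change.** In SAP 7.11.2 and Table 9, prespecify a Cycle 1 table of TEAEs, SAEs and Grade 3 or higher events, by treatment received in Cycle 1, as the main between-arm adverse event comparison.

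- **Window.** Count events by onset date, from first dose to the earliest of a fixed day common to both arms, start of Cycle 2, crossover, or other AML therapy.
- **Fixed day.** Keep it within required SAE reporting in both arms. Protocol 8.5 ends this 30 days after study drug, which is Day 34 for a one-cycle CM patient. Day 45, when response is assessed at the latest, can be a supplementary cut.
- **Grade.** Protocol 8.4 records only an event's highest grade, with dates for the whole event. Footnote that the grade shown may have been reached after Cycle 1.
- **Whole-study tables.** Keep them as description, add events per cycle or per patient-month, and show post-crossover events separately. Reconcile the safety grouping of crossover patients between Protocol 11.3 and SAP 7.1.

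The cost is SAP wording and a few tables from data already collected. Later-cycle events would appear only in the descriptive tables. A common window from Day 1 also gives ACM about 5 fewer days after mitoxantrone: 25 vs 30 at Day 34, and 36 vs 41 at Day 45. Patients who start Cycle 2 or other therapy before the fixed day will have shorter windows, so days at risk should be shown by arm.

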7.11.3. Classification of Tumor Lysis Syndrome

Cairo-Bishop definitions for laboratory TLS and clinical TLS will be used to diagnose and grade TLS.¹⁴ Patients are classified as experiencing laboratory TLS if they have any two or more serum values of uric acid, potassium, phosphorus and/or calcium shown in Table 8 within 3 days before or 7 days after the initiation of study drug.

Table 8. Cairo-Bishop Definition of Laboratory Tumor Lysis Syndrome

Laboratory Parameter	Criteria
Uric Acid	≥476 μmol/L or 25% increase from baseline
Potassium	≥6.0 mmol/L or 25% increase from baseline
Phosphorus	≥1.45 mmol/L or 25% increase from baseline
Calcium	≤1.75 mmol/L or 25% decrease from baseline

Diagnosis of clinical TLS requires the presence of laboratory TLS and elevated serum creatinine levels, cardiac arrhythmia and/or seizures. Criteria for grading the severity of clinical TLS are presented in Appendix 1.

The numbers of patients experiencing laboratory TLS and the various severities of clinical TLS will be summarized within and between treatment arms.

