5.2.2 Within 72 Hours Prior to First Dose (Stage 1, Stage 2)

Perform the following activities and evaluations within 72 hours prior to administration of the first dose of study drug:

- Collect blood for evaluation of laboratory parameters ([Appendix D](#)):
 - Hematology
 - Full serum chemistry panel
- Collect urine sample for full urinalysis
- Collect urine or serum sample for β -hCG pregnancy test (urine or serum) for females of child-bearing potential
- Record all concomitant medications including all prescription drugs, nonprescription drugs, and nutritional supplements

Review all Inclusion/Exclusion criteria and determine if patient has met all eligibility criteria for inclusion into the study.

Refer to the Study Manual of Procedures for detailed instructions on enrollment (and randomization for Stage 2).

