5.4.1 Assessments Required Prior to First Dose

5.4.1.1 Cycle 1, Day 1 – At Least 10 Hours Prior to First Dose

Perform the following procedures at least 10 hours prior to dosing on Day 1:

- Physical examination including weight (kg) for calculation of body surface area (BSA)
- Assess ECOG PS (*Appendix B*)
- Initiate supportive care measures at least 10 hours prior to first dose in all patients to minimize the likelihood of tumor lysis syndrome:
 - Administer pretreatment IV hydration, oral allopurinol, and oral phosphate binder (see *Section 4.6.1*)
 - Diligent monitoring of urine output **frequently** to ensure that it equals fluid input. If input is greater than output by 10%, administration of diuretics is encouraged. Replacement of excessive fluid losses, including from diarrhea, should be done unless otherwise clinically indicated.
- Record all concomitant medications including all prescription drugs, nonprescription drugs, and nutritional supplements taken since screening.

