In general, data values will be obtained directly from the clinical database (e.g., birth date, treatment dates, AML relapse date and death date). Derivations for certain values not collected explicitly in the database are explained in relevant sections below (e.g., age and treatment failure date, sections 7.7 and 7.9.2, respectively). In some instances, it is beyond the scope of this SAP to explain schemes for patient classifications and data derivations (e.g., classifying patients in cytogenetic risk group according to published criteria). These details will be expounded in the clinical study report.

Durations of time expressed in months (e.g., times-to-event endpoints) will be reported in proportional “months” according to the formula

$$\text{months} = \frac{12}{365.25} \times \text{days}$$

Baseline value of a characteristic is defined as the last measured value prior to the first dose of study drug (or prior to randomization for patients not treated).

Statistical p-values will be truncated for display at the third digit following the decimal point. P-values less than 0.001 will be displayed as “<0.001.”

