Appendix 1. Criteria for Grading Severity of Clinical Tumor Lysis Syndrome

	Grade 1	Grade 2	Grade 3	Grade 4	Grade 5
Renal	Creatinine $\leq 1.5 \times \text{ULN}$	Creatinine $> 1.5\text{-}3.0 \times \text{ULN}$	Creatinine $> 3.0\text{-}6.0 \times \text{ULN}$	Creatinine $> 6.0 \times \text{ULN}$	Death
Cardiac Arrhythmia	Intervention not indicated	Non-urgent medical intervention indicated	Symptomatic and incompletely controlled medically or controlled with device (e.g., defibrillator)	Life-threatening (e.g., arrhythmia associated with CHF, hypotension, syncope, shock)	Death
Seizure	—	One brief generalized seizure; seizure(s) well controlled by anticonvulsants or infrequent focal motor seizures not interfering with activities of daily living	Seizure in which consciousness is altered; poorly controlled seizure disorder; with breakthrough generalized seizures despite medical intervention	Seizures of any kind which are prolonged, repetitive or difficult to control (e.g., status epilepticus, intractable epilepsy)	Death

Clinical TLS requires one or more clinical manifestations (renal, cardiac, neuro) along with criteria for laboratory TLS

Maximal clinical manifestation defines the severity grade

ULN = upper limit of normal; 14.4 and 105.6 $\mu\text{mol/L}$ will be used for males and females, respectively, if ULN is not available for an institution

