30-Day Mortality[a] 95% CI	xx.x% (xx.x%, xx.x%)	xx.x% (xx.x%, xx.x%)
Number of Deaths	xx	xx
60-Day Mortality[a] 95% CI	xx.x% (xx.x%, xx.x%)	xx.x% (xx.x%, xx.x%)

[a] derived from Kaplan-Meier curves for Overall Survival
SAS v9.4 (dd-mmm-yyyy hh:mm) from ADxx, ADxx, ADxx

Blueprint for high-level safety summary (include additional page to show [1] TEAE leading to a reduction in the protocol-specified dose of study drug, [2] TEAE leading to discontinuation of study drug, and [3] TEAE leading to withdrawal from the study)

Study TPI-ALV-201

Numbers of Patients with Adverse Events
(Safety Patient Population)

Page 1 of 2

Number of Patients with any...	ACM (n=xxx)	CM (n=xxx)	All Patients (n=xxx)
TEAE			
Grade 5	xxx (xx.x%)	xxx (xx.x%)	xxx (xx.x%)
Grade 4 or Higher	xxx (xx.x%)	xxx (xx.x%)	xxx (xx.x%)
Grade 3 or Higher	xxx (xx.x%)	xxx (xx.x%)	xxx (xx.x%)
Grade 2 or Higher	xxx (xx.x%)	xxx (xx.x%)	xxx (xx.x%)
Any Grade	xxx (xx.x%)	xxx (xx.x%)	xxx (xx.x%)
Treatment-Related TEAE			
Grade 5	xxx (xx.x%)	xxx (xx.x%)	xxx (xx.x%)
Grade 4 or Higher	xxx (xx.x%)	xxx (xx.x%)	xxx (xx.x%)
Grade 3 or Higher	xxx (xx.x%)	xxx (xx.x%)	xxx (xx.x%)
Grade 2 or Higher	xxx (xx.x%)	xxx (xx.x%)	xxx (xx.x%)
Any Grade	xxx (xx.x%)	xxx (xx.x%)	xxx (xx.x%)
Treatment-Emergent SAE	xxx (xx.x%)	xxx (xx.x%)	xxx (xx.x%)
TEAE Leading to a Delay in the Administration of Study Drug	xxx (xx.x%)	xxx (xx.x%)	xxx (xx.x%)

TEAE = Treatment-Emergent Adverse Event; SAE = Serious Adverse Event

SAS v9.4 (dd-mmm-yyyy hh:mm) from ADxx, ADxx, ADxx

Blueprint for TLS incidence rates by Cairo-Bishop severity grade

Study TPI-ALV-201 Tumor Lysis Syndrome Incidence Rates During [Cycle 1 | Study] Page 1 of 1
by Maximum Cairo-Bishop Severity Grade

(Safety Patient Population)

Number of patients with...	ACM (n=xxx) xxx (xx.x%)	CM (n=xxx) xxx (xx.x%)	All Patients (n=xxx) xxx (xx.x%)
No TLS	xxx (xx.x%)	xxx (xx.x%)	xxx (xx.x%)
Laboratory TLS[a]	xxx (xx.x%)	xxx (xx.x%)	xxx (xx.x%)
Clinical TLS			
Grade 1	xxx (xx.x%)	xxx (xx.x%)	xxx (xx.x%)
Grade 2	xxx (xx.x%)	xxx (xx.x%)	xxx (xx.x%)
Grade 3	xxx (xx.x%)	xxx (xx.x%)	xxx (xx.x%)
Grade 4	xxx (xx.x%)	xxx (xx.x%)	xxx (xx.x%)
Grade 5	xxx (xx.x%)	xxx (xx.x%)	xxx (xx.x%)

[a]Without clinical manifestations

SAS v9.4 (dd-mmm-yyyy hh:mm) from ADxx, ADxx, ADxx, ADxx

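### The laboratory TLS rule in SAP 7.11.3 can score a pre-dose fall in uric acid, phosphorus or potassium as tumor lysis, because the window opens before the baseline draw

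*SAP*

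**What the plan says.** SAP 7.11.3 defines laboratory TLS as "any two or more serum values of uric acid, potassium, phosphorus and/or calcium shown in Table 8", where the values fall "within 3 days before or 7 days after the initiation of study drug". Each Table 8 criterion pairs an absolute cut-off with a relative one. For uric acid it is "≥476 μmol/L or 25% increase from baseline". Phosphorus (1.45 mmol/L) and potassium (6.0 mmol/L) have the same form, and calcium has the mirror image with a 25% decrease.

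The introductory text of SAP section 7 fixes the reference point: "Baseline value of a characteristic is defined as the last measured value prior to the first dose of study drug". SAP section 3 and Protocol 11.1 define it in the same way.

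The protocol sets the order of the pre-dose samples:

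- Protocol 5.2.2: "Perform the following activities and evaluations within 72 hours prior to administration of the first dose of study drug". The list includes the full serum chemistry panel. Appendix D shows that this panel contains uric acid, phosphorus, potassium and calcium.
- Protocol 5.3.1.1 (Stage 1) and 5.4.1.1 (Stage 2), at least 10 hours before dosing: "Administer pretreatment IV hydration, oral allopurinol, and oral phosphate binder".
- Protocol 5.3.1.2 and 5.4.1.2, just before dosing: the tumor lysis labs are drawn again.

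On clinical TLS, 7.11.3 requires laboratory TLS plus elevated creatinine, arrhythmia and/or seizure. SAP Appendix 1 then grades severity. Its renal Grade 1 cell is creatinine up to 1.5 × ULN, with no lower limit.

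**The concern.** The window opens up to three days before the point that serves as baseline, and prophylaxis aimed at uric acid and phosphorus starts in between. A screening value can therefore exceed baseline by 25% because the analyte came down. For uric acid, phosphorus and potassium, that is the only way a pre-dose value can meet the percent criterion. The rule would then record effective prophylaxis as laboratory TLS before any study drug has been given.

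The presence and severity of TLS is a named safety endpoint in SAP Table 1, and Protocol 4.6.1.1 treats rapid hyperkalemia and TLS as a particular concern with alvocidib. Prophylaxis is mandatory in all arms in Cycle 1, so false positives would arise under ACM and CM alike. They would raise both rates and shrink the difference between them.

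The rule also sits badly with the SAP's own outputs. Table 9 plans one TLS table for Cycle 1 and another for the whole study, but SAP section 3 starts Cycle 1 at the first dose. A patient classified only on pre-dose values meets 7.11.3 yet has no qualifying value in Cycle 1, and no rule says what the programmer should do.

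**Working it through.** The plan states no figure to reproduce, so the check applies the rule literally to the protocol's sample schedule.

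**Step 1: threshold.** Let S be the screening value and B the value just before dosing (the baseline). S meets the percent criterion when (S − B)/B ≥ 0.25, so S ≥ 1.25 B, or B/S ≤ 1/1.25 = 0.80. That is a fall of 1 − 0.80 = 20% or more from screening to baseline.

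**Step 2: worked example (assumed values).**

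| Analyte | S | B | Fall, (S−B)/S | Rise versus baseline, (S−B)/B | Absolute cut-off reached? |
|---|---|---|---|---|---|
| Uric acid, µmol/L | 420 | 320 | 23.8% | 31.3% | No (476) |
| Phosphorus, mmol/L | 1.40 | 1.10 | 21.4% | 27.3% | No (1.45) |

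Two criteria are met, so the patient has laboratory TLS before the first dose. If the percent criteria apply only to values after the first dose, this pair contributes none.

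**Step 3: how often.** The documents contain no analyte data, so the inputs below are assumptions.

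*Model A, normal changes, independent.* Uric acid and phosphorus each have an SD of 15 points; potassium has a mean fall of 3% and an SD of 10 points. With a, b and c the chances that uric acid, phosphorus and potassium fall by at least 20%, the chance of at least two is ab + ac + bc − 2abc. For mean falls of 10% and 5%: a = Φ(−10/15) = 0.2525, b = Φ(−15/15) = 0.1587, c = Φ(−17/10) = 0.0446. The result is 0.0401 + 0.0113 + 0.0071 − 0.0036 = 0.055.

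| Mean fall, uric acid / phosphorus | At least two criteria met pre-dose |
|---|---|
| 10% / 5% | 5.5% |
| 15% / 10% | 11% |
| 20% / 15% | 21% |
| 25% / 20% | 34% |

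*Model B, lognormal changes, uric acid and phosphorus only.* Same median fall in both, log-SD 0.1 to 0.2, correlation 0 to 0.5.

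| Median fall in both | Both criteria met pre-dose |
|---|---|
| 0% | 0–5% |
| 10% | 1–14% |
| 20% | 25–33% |
| 30% | 56–85% |

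The spread shows that the frequency is driven by the assumed fall. Nothing in the documents fixes that fall.

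**Step 4: effect on the contrast.** If a share f of patients in each arm is flagged regardless of true status, the observed rate is f + (1 − f)p. The observed difference is then (1 − f)(p_ACM − p_CM). With f = 11%, it is 89% of the true difference.

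**Step 5: creatinine.** A creatinine of 80 µmol/L is 80/105.6 = 0.76 × the fallback ULN for females in Appendix 1. It fits the open-ended Grade 1 cell, but it is not elevated, so 7.11.3 does not make it clinical TLS. The two places disagree only if Appendix 1 is programmed without the sentence in 7.11.3.

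**The case against.** The best counter-argument is linguistic: a value drawn before baseline cannot have increased from it, so the percent criteria must mean post-baseline values. The SAP's shift-table definition does pair baseline with post-baseline results. The pre-dose part of the window would still have a purpose through the absolute cut-offs. This reading is sensible and may be what was intended. But 7.11.3 does not state it, its window expressly includes pre-dose days, and the shift-table definition governs a different output. The Cycle 1 definition may keep pre-dose values out of the Cycle 1 table. It does not do so for the whole-study table.

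Four further points stand:

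- The frequency rests wholly on assumed inputs, and no passage supports large falls over the interval between the two draws.
- Protocol Table 4 reports TLS in 9% to 32% of patients in three earlier FLAM studies, but gives no definitions, so those rates are not a usable yardstick.
- The classification feeds no hypothesis test. TLS is also captured through adverse events flagged by the standardized MedDRA query, which must start or worsen after the first dose, and through laboratory summaries.
- SAP 7.11.3 names a published classification, so any change to how it is applied should be declared as a study-specific rule.

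A reader might infer from Appendix 1 that normal creatinine counts as Grade 1 clinical TLS, and that the row for laboratory TLS without clinical manifestations would be empty. The documents do not support this. SAP 7.11.3 requires elevated creatinine, arrhythmia or seizure before anything is graded, and the Appendix 1 footnote also requires a clinical manifestation.

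**Conclusion.** The concern holds for laboratory TLS on a literal reading: a pre-dose fall of at least 20% in two of uric acid, phosphorus and potassium meets the rule, and the protocol's sampling order allows it to happen. The size is unknown. Under the assumptions shown it runs from near 0% to over 30% of patients, and higher still only if both analytes typically fall by 30%. The expected effect is inflated TLS incidence in both arms and a diluted ACM-CM contrast in a named safety summary, together with an unresolved conflict with the Cycle 1 table. The primary CR comparison, the sample size and the other efficacy tests are unaffected.

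The creatinine issue is secondary. The Grade 1 cell has no lower bound and *elevated* has no numeric cut-off, so the two need to be reconciled; the text of 7.11.3 already keeps normal creatinine out of clinical TLS.

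**What to change.** In SAP 7.11.3, state that the percent-change criteria apply only to values after the first dose, and that pre-dose values count only through the absolute cut-offs. Note this as a study-specific application of the named classification. Patients already above an absolute cut-off before dosing would still be counted, so the Cycle 1 table should say whether it includes them.

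In Appendix 1, give renal Grade 1 a lower bound that matches 7.11.3, for example above ULN and up to 1.5 × ULN, and use the same cut-off for *elevated* in 7.11.3.

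The cost is a few sentences and one change to a derivation, with no effect on patient care or data collection. Reported TLS rates can only stay the same or fall. The change should be made before database lock, so that the choice of rule cannot look data-driven.
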